7.4 Analysis Populations

All subjects who are randomized and dispensed investigational product will be included in the Intent-to-Treat analysis set. All subjects who are randomized, receive at least one (1) confirmed dose of investigational product, and have at least one (1) post-baseline safety assessment will be included in the Safety analysis set.

7.5 Sample Size Determination

Sample size is based on clinical judgement and deemed adequate to successfully demonstrate these goals.

4. ASSESSMENT OF SAFETY

8.1 Safety Evaluations and Criteria

As detailed in sections 5.6.1 and 5.6.2, local tolerability will be evaluated by recording the severity of the signs of AD as well as subjective symptoms of pain, burning, or stinging on treated areas involved with AD. In addition, adverse events will be documented.

8.2 Adverse Event

An AE refers to any untoward medical occurrence in a subject administered a pharmaceutical product, whether or not considered investigational product related. An AE can be any unfavorable and unintended sign (e.g., including an abnormal laboratory finding), symptom, or disease temporally associated with the use of the investigational product, whether or not it is considered to be investigational product related. This includes any newly occurring event or previous condition that has increased in severity or frequency since the administration of investigational product (treatment-emergent).

8.3 Serious Adverse Event

A serious adverse event (or adverse reaction, or suspected adverse reaction) refers to any AE, occurring at any dose level and regardless of causality that:

• Results in death.

DermBiont

- Is life-threatening: Life-threatening means that the subject was at immediate risk of death from the event as it occurred, (i.e.it does not include a reaction which hypothetically might have caused death had it occurred in a more severe form).
- Results in inpatient hospitalization or prolongation of an existing hospitalization.
- Results in persistent or significant incapacity, or disability, or substantial disruption of the ability to perform normal life functions.
- Is a congenital anomaly or birth defect.
- Is an important medical event: an important medical event is an event that may not result in death, be life-threatening, or require hospitalization but may be considered an SAE when, based upon appropriate medical judgment, it may jeopardize the subject and may require medical or surgical intervention to prevent one of the outcomes listed in the definitions for SAEs. Examples of such medical events include allergic bronchospasm requiring treatment in an emergency room, a physician's office or clinic, or at home, blood dyscrasias or convulsions that do not result in inpatient hospitalization, or the development of drug dependency or drug abuse.
- A hospitalization for an elective procedure will not be considered an SAE.

8.4 Unexpected Adverse Event

An AE (or a suspected adverse reaction) is deemed unexpected if it is not reported in the Investigator's Brochure (IB), is not listed at the specificity or severity that has been observed or is not consistent with the risk information described in the general investigational plan or elsewhere in the current IND studies.

8.5 Relationship of Adverse Events to Investigational Product

The following classifications should be used when evaluating the relationship of AEs and SAEs to the investigational product.

- 1. Unrelated: No relationship between the experience and the administration of investigational product; related to other etiologies such as concomitant medications or subject's clinical state.
- 2. Probably not related: The current state of knowledge indicates that a relationship is unlikely.
- 3. **Possibly related**: A reaction that follows a plausible temporal sequence from administration of the investigational product and follows a known response pattern to the suspected investigational product. The reaction might have been produced by the subject's clinical state or other modes of therapy administered to the subject.
- 4. **Probably related**: A reaction that follows a plausible temporal sequence from administration of the investigational product and follows a known response pattern to the suspected

investigational product. The reaction cannot be reasonably explained by the known characteristics of the subject's clinical state or other modes of therapy administered to the subject.

5. **Definitely related**: A reaction that follows a plausible temporal sequence from administration of the investigational product and follows a known response pattern to the suspected investigational product and can be confirmed with a positive re-challenge test or supporting laboratory data.

8.6. Intensity: Classification of Intensity of Adverse Event.

The following classifications should be used when evaluating the intensity of AE's and SAE's:

- 1. Mild: Awareness of sign or symptom, but easily tolerated
- 2. Moderate: Discomfort enough to cause interference with normal daily activities
- 3. Severe: Inability to perform normal daily activities
- 4. Life-threatening: Immediate risk of death from the reaction as it occurred
- 5. Death

PROCEDURES FOR ADVERSE EVENT RECORDING AND REPORTING

Emergency Sponsor Contact

In the event of a medical emergency (i.e., an event that requires immediate attention regarding the treatment of a subject, operation of the clinical study, and/or the use of investigational drug), investigational site personnel must immediately contact the Medical Monitor.

Medical Monitor Contact		
Name:	MD, MS, MPH (primary)	
Telephone:		
\times		
Name:	(secondary)	
Telephone:		
$\times \times$	$\times \times \times \times \times \times \times$	

Other Required Safety Assessments

A clinically significant worsening from Baseline of any abnormal study assessment should be considered an AE and recorded accordingly. If possible, a diagnosis for the clinically significant study assessment should be provided by the Investigator (e.g., Urinary tract infection or anemia). In the absence of a diagnosis, the abnormal study assessment itself should be listed as the AE (e.g., bacteria in urine or decreased hemoglobin).

DermBiont

An abnormal study assessment is considered clinically significant if the subject has one or more of the following related to the abnormal study assessment:

- 1. Concomitant clinical signs or symptoms.
- 2. Further diagnostic testing or medical/surgical intervention.
- 3. Discontinued from the study.

Repeat testing to determine whether the result is abnormal, in the absence of any of the above criteria, does not necessarily meet clinically significant criteria. The determination of whether the study assessment results are clinically significant must be made by the Investigator.

SPECIAL REQUIREMENTS AND PROCEDURES

Study Monitoring

The Clinical Monitor and/or the Sponsor representative will arrange to visit the Investigator sites at regular intervals during the study. The monitoring visits must be conducted according to the applicable International Conference on Harmonization (ICH) and Good Clinical Practice (GCP) guidelines to ensure protocol adherence, quality of data, drug accountability, compliance with regulatory requirements, and continued adequacy of the investigational site and its facilities. During these visits, CRFs, source documents and other data related to the study will be reviewed and any discrepancies or omissions will be resolved. The Clinical Monitor will be given access to study relevant source documents (including medical records) for purposes of source data verification.

During and/or after completion of the study, quality assurance officers named by DermBiont or the regulatory authorities may wish to perform on-site audits. The Investigator is expected to cooperate with any audit and aid and documentation (including source data) as requested.

Audits and Inspections

The Investigators and clinical sites will permit study related monitoring, audits, IRB/IEC review, and regulatory inspections as requested by the regulatory authorities, DermBiont or designee, including direct access to source data/documents (i.e., original medical records, laboratory reports, hospital documents, progress reports, signed Informed Consent Forms (ICFs), etc.) in addition to eCRFs.

Data Quality Control and Quality Assurance

The Investigator is responsible for ensuring the study is conducted according to the protocol, Code of Federal Regulations (CFR), GCP, and applicable regulatory requirements. The responsibilities

DermBiont

outlined in these documents along with the identification that a signed informed consent must be obtained prior to a subject participation in the study.

Confidentiality

To maintain subject privacy, all eCRFs, study samples, investigational product accountability records, study reports and communications will identify the subject by the assigned subject identification number. The Investigator will grant monitor(s) and auditor(s) from DermBiont or designee and regulatory authority(ies) access to the subject's original medical records for verification of data gathered on the eCRFs and to audit the data collection process. The subject's confidentiality will be maintained and will not be made publicly available to the extent permitted by the applicable laws and regulations.

All information regarding the investigational product supplied by DermBiont to the Investigator is privileged and confidential information. The Investigator agrees to use this information to accomplish the study and will not use it for other purposes without consent from DermBiont Inc. It is understood that there is an obligation to provide DermBiont with complete data obtained during the study. The information obtained from the clinical study will be used towards the development of the investigational product and may be disclosed to regulatory authority(ies), other Investigators, corporate partners, or consultants as required.

Subject Rights

Study subjects can withdraw their consent to have their clinical samples stored even after the sample has been shipped to the sponsor laboratory. A study subject should contact the Investigator or the Investigator's designee and ask for his/her sample to be withdrawn from the storage and destroyed. For samples that have been partially analyzed the remaining sample will be destroyed but the clinical site and DermBiont shall be entitled to retain and use any research results obtained prior to the withdrawal of consent.

Protocol Amendments

Protocol amendments that impact subject safety, change the scope of the investigation, or affect the scientific quality of the study must be approved by the IRB/IEC and submitted to the appropriate regulatory authorities before implementation of such modifications to the study.

In the event that the protocol needs to be modified immediately to eliminate an apparent hazard to a subject, DermBiont will amend and implement the protocol change and subsequently notify the regulatory authorities and/or the IRB/IEC, as appropriate.

The Investigator should not modify the protocol without agreement from DermBiont and prior review or approval by the IRB/IEC. Any deviations from the protocol should be documented by the Investigator or designee.

Obligations of the Clinical Investigator

The Investigator will agree to be responsible for the overall conduct of the study; for completing regulatory documents and documentation of training; for ensuring that the study is conducted according to the study protocol; for protecting the rights, safety and welfare of study subjects under their care; and for insuring data quality and integrity.

If any study responsibilities are delegated, the Investigator will be responsible for maintaining written documentation of who is designate to perform the specific responsibilities.

The study will be conducted by qualified study Investigators.

The Investigator or designees are responsible for qualified subjects and collecting samples. The Investigator or designees will be responsible for maintaining records of all samples collected and investigational product administrations; recording the subject's data on the source documents and CRFs; documenting the presence or absence of AEs following sample collection and investigational product applications and following the reporting requirements of any SAEs to the Sponsor and IRB/IEC.

Institutional Review Board/Independent Ethics Committee

The Investigator must obtain written IRB/IEC approval of the protocol, approval for relevant supporting information and all types of subject recruitment and advertisement and the ICF prior to starting the study. The IRB/IEC will meet all US FDA requirements governing IRBs/IECs (21 CFR Part 56).

DermBiont or the designee must approve the ICF submitted to the investigational site's IRB/IEC. All subject recruitment and advertisements must be submitted to DermBiont or designee prior to submission to the IRB/IEC, for review.

Ethical Conduct of the Study

DermBiont and the Investigator must comply with all instructions, regulations, and agreements in this protocol and in the applicable ICH and GCP guidelines and must also conduct the study in accordance with local regulations.

Written Informed Consent

Written informed consent is required from each subject prior to any testing under this protocol, including screening tests and evaluations. The ICF, as specified by the investigational site's IRB/IEC, must follow the Protection of Human Subjects regulations listed in 21 CFR Part 50.

The background of the proposed study and the benefits and risks of the procedures and study must be explained to the subjects. It is the responsibility of the Investigator to obtain consent and to provide the subject with a copy of the signed and dated ICF. Confirmation of a subject's informed consent must also be documented in the subject's medical record prior to any testing under this protocol, including screening tests and evaluations.

All ICFs used in this study must be approved by the appropriate IRB/IEC and by DermBiont, or designee. The ICF must not be altered without the prior agreement of the relevant IRB/IEC and DermBiont.

Subject Data Protection

Prior to any testing under this protocol, including screening tests and evaluations, subjects must authorize the release and use of protected health information (PHI), as required by local law.

DATA HANDLING AND RETENTION OF RECORDS

Paper and Electronic Case Report Form Completion

Paper CRF and eCRFs will be completed for each enrolled subject. It is the Investigator's responsibility to ensure the accuracy, completeness, and timeliness of the data reported in the subject's paper and eCRF. Source documentation supporting the paper and eCRF data should indicate the subject's participation in the study and should document the dates and details of study procedures, AEs, and subject status.

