1.2 Rationale

In-vitro has been shown to significantly inhibit the growth of *S. aureus* (DR005 2019) most frequently associated with AD. Application of to the skin of amphibians has been shown to be able to treat and prevent the acquisition of a lethal cutaneous fungal infection. (Harris et al. 2009). In a previous small pilot clinical trial, a single application of DBI001 was well tolerated and resulted in the reduction in the abundance of *S. aureus* and improvement in the signs and symptoms of AD, most noticeable pruritis (DBI-CSR-203). In a clinical trial of subjects with T. pedis 28 daily applications of DBI001 to the entire foot was well tolerated, decreased the abundance of T. rubrum, and improved the signs and symptoms of T. pedis. (DBI-CSR-201, DBI-CSR-204) Based on these observations, topical application of the probiotic has the potential to be a novel approach to the treatment of AD.

POTENTIAL RISKS AND BENEFITS

Potential Risks

Despite the fact that is found in the cutaneous microbiome of some people as well as in the human food chain, it is possible that application of could result in a worsening of the AD, impetigo, folliculitis, or cellulitis. It is possible that could be an opportunistic pathogen in severely immune compromised subjects. PBS solution will be used to collect samples and it could cause a local irritant reaction

As detailed in the Investigator's Brochure, if worsening of the AD, impetigo, or folliculitis or cellulitis were to occur, is susceptible to commonly used topical and oral antimicrobials and antibiotics.

Potential Benefits

It is possible that daily applications of could result in improvement in the subject's AD. Such a treatment also has the potential to decrease the use of oral and topical antibiotics.

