Cephalosporins, Quinolones, Tetracyclinea, Aminoglycosides Macrolides, Carbapenems and Lipopeptides.

11. Willingness to allow digital photos of treatment areas to be taken and stored.

Exclusion Criteria

The following are the exclusion criteria that will exclude subjects from enrolling into the trial:

- 1. Women who are pregnant, planning a pregnancy, breastfeeding or have a positive pregnancy test at screening.
- 2. Any dermatological conditions that could interfere with clinical evaluations or any disease state or physical condition which might expose the subject to an unacceptable risk by study participation.
- 3. Any underlying disease(s) or other dermatological conditions that require the use of exclusionary topical or systemic therapy.
- 4. Spontaneously improving or rapidly deteriorating dermatitis anywhere on the body.
- 5. Netherton's syndrome or other genetic dermatoses that result in defective epidermal barrier function.
- 6. Treatment of any type of cancer within the last 6 months other than cutaneous basal cell carcinoma.
- 7. History of any significant internal disease (which contraindicates use of live microbiome e.g. leukemia, liver failure, cardiovascular disease).
- 8. Subjects who are known to be allergic to any of the test product(s) or any components in the test product(s) or have a history of hypersensitivity or allergic reactions to any of the study preparations as described in the Investigator's Brochure.
- 9. AIDS or AIDS related complex by medical history.
- 10. Known or suspected immune suppressive medications or diseases or any condition that in the opinion of the investigator would increase the subject's susceptibility to opportunistic infections.
- 11. Treatment with systemic immune modulating or anti-inflammatory biologics agents within 16 weeks of Baseline Visit.
- 12. Poorly controlled diabetes mellitus Type I or II by medical history.

- 13. Peripheral vascular disease based on medical history.
- 14. Any subject not able to meet the study attendance and telemed visit requirements.
- 15. Participants with a history of psychiatric disease or history of alcohol or drug abuse that would interfere with the ability to comply with the study protocol.
- 16. Subjects who have participated in any other trial of an investigational drug or device within 30 days prior to enrollment or participation in a research study concurrent with this study.

Recruitment and Retention

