6.4.1 Subject Withdrawal

Participation in the study is strictly voluntary. A subject has the right to withdraw from the study at any time for any reason and is under no obligation to disclose the reason. If a subject withdraws, the Investigator and Sponsor are to be informed immediately and the withdrawal documented accordingly. Subjects may be replaced at the discretion of the Investigator and/or Sponsor.

The Investigator has the right to terminate participation of a subject at any time for any of the following:

- Use of non-permitted concomitant medication
- Lack of subject compliance
- Protocol violation
- Disease progression
- Any perceived safety risks

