6.4.3 Stopping Rules

The sponsor (Medical Director/Chief Medical Officer) will halt the study for a review of the safety data if there are safety concerns noted for any reason and if one or more subjects experience two AE's assessed as a Grade 3 (severe) or higher, of the same type that is considered possibly, probably or definitely related to the IP.

Study Visits

The study will be conducted with a Screening visit, Day 1 / Baseline visit, Study Day visits 7, 14, 21, 28 and two follow-up visits on Days 35 and 42.

If reported violations of treatment site restrictions occurred prior to the visit at Screening, Day 1 / Baseline, Day 7, 14 or 21, details of the violation should be recorded in the CRF and the evaluations and sampling completed as scheduled.

If reported violations of treatment site restrictions occurred less than 24 hours prior to the visit at Day 28, 35, or 42, details of the violation should be recorded in the CRF and evaluations can be completed, but an additional visit 24-48 hours after the violation should be scheduled for sample collections. However, if reported violations of treatment site restrictions occurred more than 24 hours prior to the visit at Day 28, 35, or 42, details of the violation should be recorded in the CRF and the evaluations and sampling completed as scheduled.

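### Section 8.5 makes a known response pattern a condition of every related grade, so the causality scale has no grade for a plausibly timed adverse event of a new kind

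*Combined protocol and SAP*

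**What the plan says.** Section 8.5 gives one causality scale for all AEs and SAEs. Its five grades are unrelated, probably not related, possibly related, probably related and definitely related. The last three share a core: "A reaction that follows a plausible temporal sequence from administration of the investigational product and follows a known response pattern to the suspected investigational product". They differ only in what follows. Possibly related allows that the subject's condition or another therapy may be the cause. Probably related says that these cannot reasonably explain the event. Definitely related adds a positive re-challenge or supporting laboratory data. The term *known response pattern* is not defined, and the scale has no unknown or not-assessable grade.

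Two other parts of the protocol use these grade names:

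- Section 6.4.3 (Stopping Rules) has the sponsor halt the study for a safety review "if there are safety concerns noted for any reason and if one or more subjects experience two" AEs of Grade 3 or higher, "of the same type that is considered possibly, probably or definitely related to the IP".
- Section 7.3.2 (Adverse Events) summarizes TEAEs and SAEs by relationship to the product. In the TEAE summary by relationship, each subject counts once per system organ class or preferred term, at the greatest causality.

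Section 8.4 separately treats an AE or suspected reaction as unexpected if the Investigator's Brochure does not report it.

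**The concern.** A causality scale should be able to record that a new kind of reaction might be due to the product. Here even the lowest related grade requires that the reaction already be recognised as a response to the product. Section 8.4 foresees suspected reactions that are absent from the Brochure, yet section 8.5 gives them no related grade.

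The point has some force for this product. DBI-001 is a live bacterial gel whose inhibitory mechanism the Background describes as not yet known. The AD experience cited under Rationale is a small single-application pilot, in adults according to its title in the reference list. This trial gives 27 daily doses to subjects from age 12. The Rationale also cites 28 daily applications in tinea pedis, but on a different disease.

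What is at stake is consistency between investigators at multiple centres. The same event can be graded on either side of the line that decides whether section 6.4.3 counts it and which relationship row of section 7.3.2 it falls in.

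**Working it through.** No figure in the plan is in dispute, so the check is logical. Take an AE with plausible timing, no recognised pattern for the product, and a relationship that is neither established nor excluded. Compare it with each grade in section 8.5.

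| Grade | What the wording requires | Met? | Counted in 6.4.3? |
|---|---|---|---|
| Unrelated | no relationship; another etiology | No: a relationship is not excluded | No |
| Probably not related | current knowledge points to an unlikely relationship | No: absence of knowledge is not evidence against | No |
| Possibly related | timing and known pattern; another cause may apply | No: pattern fails | Yes |
| Probably related | timing and known pattern; no other reasonable cause | No: pattern fails | Yes |
| Definitely related | timing and known pattern; confirmation | No: pattern fails | Yes |

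**Grades.** The clause stands in 3 of 5 grades, and these are exactly the 3 that section 6.4.3 names. The event meets 0 of 3 related grades and 0 of 5 grades overall. The scale is therefore incomplete. It does not send the event to a not-related grade; it leaves the investigator to pick the nearest one.

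**Which events are affected.** The gap excludes anything the documents already foresee, if foreseen reactions are accepted as known patterns. Section 6.6.1 covers the five ADSI signs and symptoms and application site reactions, and section 6.6.2 adds pain, burning and stinging. Potential Risks says that application "could result in a worsening of the AD, impetigo, folliculitis, or cellulitis" and that the organism "could be an opportunistic pathogen in severely immune compromised subjects". Exclusion criterion 10 refers to "susceptibility to opportunistic infections", and criterion 8 to "hypersensitivity or allergic reactions to any of the study preparations as described in" the Brochure. The Brochure is not among the documents and may list more, so no example of an event in the gap can safely be named.

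**What follows from a strict grading.** If a Grade 3 event is graded not related, it is not counted in section 6.4.3. It also leaves the related rows of section 7.3.2. With about 20 subjects, one reclassified subject moves a related-TEAE percentage by 1/20 = 5 percentage points, assuming that subject has no other related event in the same category.

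**What does not depend on a related grade.**
- Section 6.4.2 allows discontinuation of the study for AEs unusual in nature.
- Section 6.4.1 allows the investigator to end a subject's participation for "Any perceived safety risks".
- Section 8.3 defines SAEs whatever their cause, and the obligations of the clinical investigator include reporting them to the sponsor and the IRB/IEC.
- The emergency contact section requires immediate contact with the Medical Monitor.
- Section 7.3.2 lists every AE by subject.

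Life-threatening and fatal intensities meet the SAE definition, so such events reach the sponsor however they are graded. What remains exposed is the formal count and the relationship rows.

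**The case against.** The strongest reply is that investigators will use judgement. *Known response pattern* is undefined, so it can be read loosely. Possibly related is also the nearest fit, since it matches on timing and openly allows another cause. The stopping rule does not cite section 8.5, and what counts as known may be set out in the Brochure. Most plausible reactions are foreseen, and several safeguards work without a causality grade.

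Much of this stands. It limits the harm and rules out any claim about frequency. It does not remove the gap: section 8.5 says its classifications are the ones to use, nothing elsewhere in the protocol relaxes the condition, and a loose reading by some investigators beside a strict reading by others is the inconsistency at issue.

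A reader might infer more than the documents support:

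- *That a new kind of reaction must be graded not related.* The text does not prescribe this, because the not-related grades do not fit either. Exclusion from the count is one possible outcome.
- *That the clause alone would prevent a halt.* Section 6.4.3 joins a noted safety concern and the event count by *and*. Read literally, the count is necessary but not sufficient. The concern limb is then not an independent backstop either, which is a separate matter.
- *That sections 8.4 and 8.5 contradict each other.* One defines expectedness and the other causality. They are in tension only for a suspected reaction of a new kind.
- *That the number of foreseen reactions measures the gap.* Those reactions lie outside it, and the protocol does not say that a foreseen risk is a known pattern.

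**Conclusion.** The point holds as a defect of wording. The section 8.5 scale has no grade for a plausibly timed AE that is new in kind, so its grading, and with it the section 6.4.3 count and the section 7.3.2 relationship rows, depends on how strictly each investigator reads one undefined clause. Severity is minor. Confidence is high for the wording, but lower for any effect on the count or tables. No rate or probability can be given. The conclusion assumes that the Brochure does not define the term in a way that removes the condition.

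**What to change.** In section 8.5, remove the known-pattern condition from the possibly related definition only. Plausible timing with a reasonable possibility of causation should be enough, and the subject's condition or another therapy may also explain the event. Section 6.4.3 already counts possibly related events, so this one change closes the gap. Leave probably related and definitely related as they are, since asking for a recognised pattern at higher certainty is a defensible choice.

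The cost is an edit to one definition and a short training note to sites. No endpoint, visit or sample size changes. The downside is that a few more events may be graded possibly related, so the relationship table may look slightly less favourable.
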